### **6.1 Primary Objective**

1. To determine if an acute bout of passive, warm water therapy reduces plasma [glucose].

### **6.2 Secondary Objectives**

*To determine:*

1. whether plasma [glucose] reduces more if the passive, warm water therapy is conducted before or after the OGTT?
2. whether plasma [insulin] reduces more if the passive, warm water therapy is conducted before or after the OGTT?
3. whether insulin sensitivity increases following an acute bout of warm water therapy?
4. whether fuel utilisation alters during and following an acute bout of warm water therapy?
5. whether cardiovascular status is altered during or after an acute bout of warm water therapy?

6. whether eHSP increases during an acute bout of warm water therapy?
7. whether inflammatory status reduces during or after an acute bout of warm water therapy?

### 6.3 Summary of Study Design

#### Recruitment

Participants will be recruited from adult diabetes outpatient clinics at the Queen Alexandra Hospital (Portsmouth), via a database of known individuals with T2DM from the Wessex, Diabetes, National Institute for Health Research (NIHR) Clinical Research Network and via posters and word of mouth at the University of Portsmouth. Only males and post-menopausal women will qualify for the study. Finally, the local Desmond diabetes awareness group meetings will be used to identify potential volunteers. Potential participants will either be approached by their T2DM consultant, the principal investigator, member of the research team or a research nurse. Following the participants declaration of interest, via telephone, mail, email or in clinic, they will be given a participant information sheet. A member of the research team will subsequently approach the participant  $\geq 48$  h later, to answer any questions and organise consent, screening and familiarisation (visit 1).

The design will be a balanced, randomised, within-subject comparison of three conditions (condition 1: OGTT in 23 °C air, condition 2: OGTT 30 min before 60 min in  $\sim 39^{\circ}\text{C}$  water ( $\sim 90\%$  RH), condition 3: OGTT 30 min after 60 min in  $\sim 39^{\circ}\text{C}$  water ( $\sim 90\%$  RH)). There will be 4 visits in total, visit 1 is for consent, screening and familiarisation and visits 2, 3 and 4 are experimental conditions.

#### Visit 1 (consent, screening and familiarisation)

During visit 1, participants will give their informed consent, followed by a health screening questionnaire. In addition to the health screening questionnaire, medical history and a blood sample will be collected and analysed for a full blood count, glycated haemoglobin (HbA1c), liver and kidney function. Finally, a resting electrocardiogram (ECG) will also be recorded and then examined for irregularities, where a clinical decision will be made on further participation to the study by consultants at QA hospital. Participants will then be shown the rest of the equipment and taken through the procedure for the next 3 visits and, if the participant is happy to continue the study, the next visit will be organised.

#### *Pre experimental instructions*

Before all experimental visits the participants will be instructed to keep their normal diet up to 48 h before coming in for their visit and also replicate it before each visit (they will be given a food diary). They will be asked to avoid exercise and hot baths / saunas 48 h before each visit (can have brief (< 5 minutes) luke-warm showers) and consume 17 mL.kg water (for examples an 80 kg male would need to drink at least 1.36L of water) and other fluids ad libitum throughout the active day ( $\sim 16$  h) [Benelam and Wyness, 2010] and 4 mL.kg upon waking the morning of the visit. All conditions will require the participant to fast for 12 h before coming

[figure not shown]
to the start of the visit. For the pre-test diet, participant will be asked to keep a normal balanced diet (they will record their intake in a diary). Participants will also be instructed on suitable clothing to wear for each visit (explained again in the PIS). In line with OGTT guidelines, participants will be asked to not take their diabetes drugs on the morning of the test (hypoglycaemic agents before the fasting period are to be taken as normal). Prior to leaving the laboratory, participants will be provided with lunch, then asked to take their tablets and blood sugars checked prior to leaving.

#### Visit 2, 3 and 4

Participants will arrive at the laboratory at ~9 am for conditions 1 and 2 and 8 am for condition 3. Prior to a 15 min resting period (supine) before any measures are taken participants will be asked to insert a rectal thermistor (participants will be given clear instructions using our SoPs). Condition 1, 2 and 3 will be balanced and participants randomly allocated to begin the study in either visit 2, 3 or 4 using a blinded member of the team.

For all visits (see figure 2), participants will lie in a semi recumbent position in minimal clothing (bathing shorts and a t-shirt) for the entirety of the visit. Initially, participants will be cannulated (Versatus winged and ported IV cannula, Terumo, Japan) and blood samples drawn for analysis of osmolality (Lithium Heparin (LH) tubes BD, USA) plasma [glucose] (Fluoride/Oxalate tubes, BD, USA), [insulin] (Ethylenediaminetetraacetic acid (EDTA) K2, BD, USA), and [eHSP70] (EDTA K2, BD, USA) at baseline and every 30 min of each experimental visit. Following cannulation an 180 min OGTT (75g) (RapiLOSE OGTT solution, Penlan healthcare, Japan) will commence in a thermoneutral room (~ 23°C). A maximum of 18 mL of blood being drawn at each time point (max 126 mL per visit). To maintain the patency of the cannula and to reduce the risk of infection, after every sample is taken, 5 mL of saline will be flushed through the cannula. Then before every sample is taken, 2.5 mL of blood will be drawn out of the cannula to ensure any remaining saline will not interfere with the samples and data interpretation (additional 17.5mL per visit). During the OGTT, HR (via electrocardiogram) will be measured continuously, whilst blood pressure (M5-1, Omron, Japan), deep body temperature (rectal probe) and resting metabolic rate (indirect calorimetry) (Quark CPET, Cosmed, Italy) will be assessed every 30 min.

Condition 2 will employ identical procedures to condition 1, except thirty minutes into the OGTT, the participant will be immersed into an immersion tank (~39°C) for 60 min. Water temperature will be manipulated as required to achieve and maintain a target  $T_{rec}$  at 38.5°C using water between 37.5 and 39°C, and then participants will be removed horizontally back into the thermoneutral room for the remainder of the OGTT. Participants will be towel dried and given a towelled robe to wear. Condition 3 will employ identical procedures to condition 2, with the exception that the heating via immersion will start as soon as the participant is instrumented (and following a 15 min rest period) and the OGTT will commence 30 min after the 60 min immersion time for a further 180 min (see figure 2 for a schematic). Finally, if willing participants will be asked to take part in a brief exit interview about their experience.

**Figure 2.** Schematic of the 3 experimental conditions. BP, thermal sensation, HRV, osmolality, insulin sensitivity, RMR, eHSP70, IL-6, IL-10, plasma glucose and insulin measured at 30 min intervals from 0930-1230 for visit 1 and 2, and from 1000-1300 for condition 3 (with the addition of a baseline measure at 0830 for visit 3). Muscle oxygenation at 0930, 1000, 1130, 1200 and 1230 for condition 1 and 2. Muscle oxygenation at 0830 and from 1000-1300 at 30 min intervals for condition 3. HR continuous for entirety of visit. Solid line indicates immersion period and dashed line indicates OGTT period.

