#### *Passive heating and Core Temp*

The passive heating conditions (conditions 2 and 3) will be conducted in a thermoneutral room (~ 23°C air, ~ 90% RH), at the same time of day, with the heating taking place for 60 min in a heated pool (starting at 39°C water). Pre and post body mass will also be recorded, along with any fluid or solids going into or out of the body. Participants will firstly be cannulated lying horizontal, then will lie semi-recumbent and baseline measures taken. Depending on which condition (either 2 or 3) the OGTT or the passive heating will start first. Passive heating will start with the participant entering the pool and lying semi-recumbent on a submerged bed with their head, neck and cannulated arm above the water. Participants' rectal temperature ( $T_{rec}$ ) will be monitored so that once it reaches ~38°C the water will be cooled to ~ 38 - 38.5°C so that it will maintain  $T_{rec}$  at ~ 38.5°C ( $T_{rec}$  is still expected to rise slightly after reduction in water temperature, see below for more details). If  $T_{rec}$  reaches 39°C or above at any point, the participant will immediately be withdrawn from the study and a cooling protocol administered (see SOP attached). Additionally, if systolic BP raises above 180 mmHg or HR above 140

bpm, participants will be immediately withdrawn from the study. Passive heating will cease by winching the participant, still lying semi-recumbent, out of the immersion tank and onto a semi-recumbent bed. The participant will then be towel dried and given a blanket (to ensure maximum heat retention) and remain semi-recumbent until completion of the visit. The remainder of the visit will be conducted in the thermoneutral room.

$T_{rec}$  will be measured continuously throughout each visit using disposable rectal thermistors (Rectal temperature probe, Philips, Netherlands). Participants will self-insert the thermistor to 15 cm (this will be marked with sterilised tape) into the rectum using standard operating procedures.  $T_{rec}$  will be closely monitored throughout the passive heating conditions to ensure that it does not exceed 39°C.

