### *OGTT and Insulin Sensitivity*

Insulin sensitivity will be calculated using values from both plasma glucose and plasma insulin. Multiple calculations for insulin sensitivity exist, each with their own strengths and weaknesses. Calculations used can be split into two categories: fasting indices and OGTT indices. A meta-analysis [Otten et al., 2014] of all the current surrogate measures of insulin sensitivity showed that the most valid fasting calculation to use compared with the gold standard HEC method, was the quantitative insulin sensitivity check index (QUICKI). Out of the OGTT surrogate insulin sensitivity measures Otten et al. (2014) highlighted 4 indices that were the most suitable surrogate for HEC: Stumvoll, OGIS, Matsuda and Gutt.

Following an overnight fast, blood samples will be taken for the measurement of fasting glucose and insulin levels, and this data will be used to calculate  $\beta$ -cell function via the QUICKI model [Katz et al., 2000],  $1/[\text{Log}(I_0)+\text{Log}(G_0)]$  ( $I$ =insulin,  $G$ =glucose,  $_0$ =baseline) which has been shown to have a strong positive correlation with the HEC [Otten et al., 2014]. Post-prandial glycaemic control will be measured by a 180 min OGTT (maximum of 75 g anhydrous glucose), with blood samples taken from a cannula at 0, 30, 60, 90, 120, 150 and 180 min of the OGTT, with  $\beta$ -cell function being calculated using the Stumvoll method (Equation 1).

$$0.226-0.0032 \times \text{BMI}-0.0000645 \times I_{120}-0.00375 \times G_{90}$$

**Equation 1.** Stumvoll's insulin sensitivity index equation [Stumvoll et al., 2000]

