Blood pressure; participants will feel a cuff squeeze their arm and this can be uncomfortable for a few moments. Blood samples taken every 30min via cannulation (using the appropriate hygienic technique and by a trained individual): Intravenous access can cause discomfort associated with insertion of the needle. Infusion of saline (5 mL.30min) will be applied to minimise infection risk (flushing and locking eliminates potential nesting sites for microorganisms) and clotting. To avoid the saline affecting subsequent samples, 2.5 mL of blood will be drawn from the cannula before they are collected.

Other risks that have been accounted for are hypotension and loss of consciousness in the water. If at any point the participants BP is measured at  $\geq 180/100$  the trial will be terminated and the participant withdrawn from the study. If there is loss of consciousness in the water the participant will immediately be harnessed securely out. This can be done quickly as they will already be lying on the sling. Once they are out of the water and placed on a bed, their breathing will be checked and first aid administered. They will also be cooled via cold water spray and a fan. Additionally, their head will never go underwater as their head will be elevated above waterline throughout all submersions.

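### The single per-visit blood maximum counts seven draws, but condition 3 has eight, so its maximum should be 144 mL plus 20 mL of discard

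*Combined protocol and SAP*

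**What the plan says.** Section 6.3 (Summary of Study Design, under the heading for visits 2, 3 and 4) sets the ceiling per draw and per visit in one sentence: "A maximum of 18 mL of blood being drawn at each time point (max 126 mL per visit". It then provides for clearing saline from the line: "before every sample is taken, 2.5 mL of blood will be drawn out of the cannula", which it totals as "additional 17.5mL per visit". Neither total is broken down by condition.

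The sampling times appear in several places.

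- Section 6.3 gives a general rule that blood is taken "at baseline and every 30 min of each experimental visit", and refers the reader to Figure 2.
- The Figure 2 caption gives clock times at 30-minute intervals. For conditions 1 and 2 they run from 0930 to 1230. The remaining condition is sampled "from 1000-1300 for condition 3 (with the addition of a baseline measure at 0830 for visit 3". The measures listed include osmolality, glucose, insulin, eHSP70, IL-6 and IL-10, all of which need blood.
- Section 9.4 (Passive heating and Core Temp) puts the baseline before either heating or the glucose drink: "Participants will firstly be cannulated lying horizontal, then will lie semi-recumbent and baseline measures taken".
- Section 9.4 (OGTT and Insulin Sensitivity) fixes the test samples, "with blood samples taken from a cannula at 0, 30, 60, 90, 120, 150 and 180 min of the OGTT".

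**The concern.** In conditions 1 and 2 the baseline sample is also the 0-minute sample of the glucose tolerance test, so seven draws cover the visit. In condition 3 they are separate. Baseline is taken before immersion, and the test does not begin until 30 minutes after the 60-minute immersion ends. The visit therefore needs one draw more than the stated maximum allows.

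What is at stake is the accuracy of a procedural limit. Staff who follow the condition 3 schedule and draw the permitted 18 mL each time would exceed the protocol's own per-visit maximum. Every participant who completes the crossover has one condition 3 visit.

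**Working it through.** **Inputs.** From Section 6.3: 18 mL ceiling per draw, 126 mL per visit, 2.5 mL discard before each sample, 17.5 mL discard per visit. From the Figure 2 caption: 0930 to 1230 for conditions 1 and 2; 0830 and then 1000 to 1300 for condition 3. From Section 9.4: test samples at 0, 30, 60, 90, 120, 150 and 180 minutes.

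**Reproducing the stated figures.**

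- Draws implied by the sample total: 126 / 18 = 7.
- Draws implied by the discard total: 17.5 / 2.5 = 7.
- Conditions 1 and 2, 0930 to 1230 every 30 minutes: 7 draws. The stated figures are correct for these visits, and they count a discard at every draw, including the first.

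**Checking the 0830 time.** The condition 3 test starts at 1000. Taking off the 30-minute gap and the 60-minute immersion gives 0830 for the start of immersion, so a baseline at 0830 fits the described sequence.

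**Counting condition 3 draws.** Baseline at 0830: 1. Test samples from 1000 to 1300 every 30 minutes: 7. Total: 8.

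**Condition 3 maximum.**

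- Samples: 8 x 18 = 144 mL, against 126 mL stated (+18 mL).
- Discard: 8 x 2.5 = 20 mL, against 17.5 mL stated (+2.5 mL).
- Together: 144 + 20 = 164 mL. The two stated figures sum to 126 + 17.5 = 143.5 mL, a total formed here and not given in the protocol.
- Difference: 164 - 143.5 = 20.5 mL; 20.5 / 143.5 = 14%.

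**Across the three experimental visits** (again sums formed here): 3 x 143.5 = 430.5 mL on the stated figures, and 2 x 143.5 + 164 = 451 mL once condition 3 is corrected. The increase is 20.5 / 430.5 = 5%.

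**The case against.** The best case for leaving the text alone is that 18 mL is a ceiling and actual draws may be smaller, so a condition 3 visit might stay under 126 mL in practice. That is possible, but 126 mL is also presented as a maximum, and it should cover the protocol's own schedule at the protocol's own ceiling. It does not.

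It could also be said that the caption attaches the 0830 baseline to visit 3, and that visit order is randomised. The sense is clear, however. Section 6.3 has participants arrive at 8 am only for condition 3, and the caption places muscle oxygenation at 0830 in condition 3. The count also stands without that phrase, because Section 9.4 requires both a baseline before heating and a 0-minute test sample.

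The discard could be held at 17.5 mL if the first draw, made before any saline flush, needed none. The text says otherwise, and the stated 17.5 mL for seven draws already counts the first.

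Several stronger readings are tempting, and the documents do not support them.

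- **Ten draws.** Taken literally from 0830 to 1300, the phrase "at baseline and every 30 min of each experimental visit", echoed in Section 14 by "Blood samples taken every 30min via cannulation", gives ten. But Section 6.3 points to Figure 2, whose caption sets specific times and omits draws at 0900 and 0930. The specific schedule governs, and the Section 14 wording describes a procedure and its risks without setting times.
- **Participants are told a wrong volume.** The 126 mL figure appears only in Section 6.3. Section 14 gives the sampling frequency and the discard per draw but no total. The information sheet is not in the reviewed text.
- **Blood pressure goes unmeasured during the condition 3 immersion.** Section 9.4 (HR and BP) sets readings every 30 minutes without restricting them to the test, so the caption's silence does not show a gap.

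**Conclusion.** The point holds and is minor. The single per-visit maximum is right for conditions 1 and 2 and one draw too low for condition 3, where it should be 144 mL of samples plus 20 mL of discard. The understatement is 20.5 mL, or 14% of the sum of the two stated figures.

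This rests on two assumptions: that the Figure 2 caption gives the intended condition 3 times, and that a discard precedes every draw, as Section 6.3 says and as its own total implies. The Figure 2 drawing and the schedule appendix were not available, so the conclusion is confined to the visible text.

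A reader might infer that a safety limit is breached or that the results are affected. Neither follows. The documents state no other blood-volume limit. The primary endpoint, glucose AUC during the test, draws on the same seven test samples in all three conditions, and the sample size and analysis do not depend on the blood volume.

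**What to change.** In Section 6.3, keep 126 mL plus 17.5 mL of discard for conditions 1 and 2, and state 144 mL plus 20 mL of discard for condition 3. In the same paragraph, align the general sampling phrase with the Figure 2 times, so that condition 3 is plainly a baseline at 0830 followed by seven samples from 1000 to 1300. If any other study document repeats the per-visit figure, change it to match.

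The cost is a wording change and a slightly less favourable stated maximum for one visit. On the caption's schedule, no procedure is added or removed.

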#### *HR and BP*

HR will be automatically calculated from the ECG, real-time. Blood pressure will be measured every 30 min via a patient monitor brachial BP cuff (Dynascope, Fukuda Denshi, Japan).

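### Section 6.3 and the Figure 2 caption schedule no blood pressure reading during the condition 3 immersion, while Section 9.4 implies about two; the sections must be reconciled because blood pressure carries a withdrawal limit

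*Combined protocol and SAP*

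**What the plan says.** Four places bear on when blood pressure is read.

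- **Section 6.3, Visit 2, 3 and 4.** The measurement sentence opens "During the OGTT, HR (via electrocardiogram) will be measured continuously, whilst blood pressure (M5-1, Omron, Japan" and ends by setting a 30 min interval for BP. For condition 3 the text says that "the heating via immersion will start as soon as the participant is instrumented (and following a 15 min rest period" and that "the OGTT will commence 30 min after the 60 min immersion time for a further 180 min".
- **Section 6.3, Figure 2 caption.** BP is in the list of measures taken at stated clock times. For the first two conditions these are "measured at 30 min intervals from 0930-1230 for visit 1 and 2"; the caption continues "and from 1000-1300 for condition 3 (with the addition of a baseline measure at 0830 for visit 3". Heart rate is listed separately, as continuous for the whole visit.
- **Section 9.4, HR and BP.** "Blood pressure will be measured every 30 min via a patient monitor brachial BP cuff". No condition or phase of the visit is named.
- **The limits.** Section 9.4, Passive heating and Core Temp, covers conditions 2 and 3 and withdraws a participant on BP or heart rate: "Additionally, if systolic BP raises above 180 mmHg or HR above 140" bpm. Section 14 also acts on BP: "If at any point the participants BP is measured at" 180/100 or above, the participant is withdrawn.

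**The concern.** A limit on blood pressure works only if blood pressure is read while the participant is exposed. In condition 3 the participant has left the water before the glucose tolerance test begins, so readings tied to the test cannot fall within the immersion. Two places in Section 6.3 tie them that way, and Section 9.4 does not.

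Two things are at stake. The first is safety monitoring: staff working from Section 6.3 and staff working from Section 9.4 would monitor the same participant differently during heating. The second is comparability. The synopsis names blood pressure among the secondary cardiovascular measures, and secondary objective 5 asks about change during as well as after heating. On the Section 6.3 schedule, BP in the water would be recorded in condition 2 but not in condition 3, and a BP excursion in the bath could be found in one heated condition and missed in the other.

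**Working it through.** This is clock arithmetic from the protocol's own times. The caption says visit where conditions are evidently meant (visit 1 is screening), and it is read that way here.

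**Inputs**

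- Condition 3 test phase: 1000 to 1300, with a baseline at 0830 (Figure 2 caption).
- Condition 3 order: 60 min immersion, then 30 min, then the test (Section 6.3).
- Conditions 1 and 2 test phase: 0930 to 1230 (Figure 2 caption).
- Condition 2 order: immersion starts 30 min into the test and lasts 60 min (Section 6.3).
- Section 9.4 interval: 30 min, unrestricted.

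**Immersion times**

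- Condition 3 end: 1000 − 30 min = 0930. Start: 0930 − 60 min = 0830. This agrees with the 0830 baseline and with an 8 am arrival followed by instrumentation and a 15 min rest.
- Condition 2 start: 0930 + 30 min = 1000. End: 1000 + 60 min = 1100.

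**BP readings after entry and up to exit**

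| Schedule | Condition 2 (1000–1100) | Condition 3 (0830–0930) |
|---|---|---|
| Section 6.3 / Figure 2 | 1030, 1100: two | none |
| Section 9.4, 30 min from 0830 | – | 0900, 0930: two |

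Under Figure 2 the condition 3 times are 0830, 1000, 1030, 1100, 1130, 1200, 1230 and 1300. The longest gap is 0830 to 1000, or 90 min: the 60 min immersion plus the first 30 min after it. If the reading at entry is counted in both conditions, the comparison is three (1000, 1030, 1100) against one (0830).

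The absence of a test-bound reading does not depend on the exact clock. Whenever condition 3 starts, the test begins 30 min after the participant leaves the water.

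**Extent if Section 6.3 is followed.** Each participant has two immersions, one of them in condition 3. With 18 completers or 20 recruited (Section 8), that is 18 to 20 of 36 to 40 immersions. If Section 9.4 is followed, the number is zero.

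**The case against.** The strongest reply is that the protocol, read whole, does provide for readings in the water. Section 9.4 sets a 30 min interval without restriction. Section 6.3 says condition 3 follows the procedures of condition 2 apart from the order of immersion and test, and condition 2 has in-water readings. The systolic limit sits in text that covers both heated conditions, and Section 14 applies its limit at any point.

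Nor is Section 6.3 reliable as an exclusive list. Its measurement sentence also places heart rate and rectal temperature within the test, although both are continuous elsewhere. The caption lists thermal sensation at 30 min times, while Section 9.4 requires it every 15 min, including during immersion. All experimental visits take place in one laboratory, whose team has the whole protocol.

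Much of this stands, and it rules out several stronger readings that a reader might infer:

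- **That the BP limits cannot be applied in condition 3.** Section 9.4 supplies readings at about 0900 and 0930.
- **That participants in that bath are unmonitored.** Heart rate and rectal temperature are continuous, and their limits operate in both immersions.
- **That a hypotension stopping rule is disabled.** Section 14 names hypotension as a risk, but the documents give no lower BP limit.
- **That objective 5 loses its during-heating part.** Heart rate and heart rate variability come from the ECG, so at most the BP component is lost.
- **That the investigators chose to omit BP in the bath.** Nothing in the documents says so.

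The reply does not remove the contradiction. For heart rate and temperature, other text expressly extends measurement to the whole visit. For BP, the caption repeats the narrow window with explicit times, and Section 9.4 neither states its span nor overrides Section 6.3. The two sections also name different BP devices (an Omron M5-1 in Section 6.3, a Fukuda Denshi Dynascope in Section 9.4), so they do not read as one procedure described twice.

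**Conclusion.** The point holds as an internal inconsistency over whether a variable with a withdrawal limit is measured during heat exposure. Section 6.3 and Figure 2 give no condition 3 reading between entry to the water and 1000, a 90 min gap, against two after entry in condition 2; Section 9.4 gives about two in condition 3. The consequence for the BP limits and for in-water BP data is conditional on Section 6.3 being the schedule used.

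The conclusion rests on immersion times derived from the text, because the Figure 2 drawing is not available. The operating procedure that Section 9.4 refers to as attached was not available either and may settle the matter in practice.

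**What to change.** Reconcile the Section 6.3 measurement sentence, the Figure 2 caption and Section 9.4 (HR and BP) with the limits in Section 9.4 (Passive heating and Core Temp) and Section 14. State one BP schedule that covers the immersion period in both heated conditions, and name the device. The choice of reading times is for the investigators, and no limit needs to change for this purpose.

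The cost is a short amendment. If the Section 9.4 interval is the one intended, it adds about two automated cuff readings per condition 3 visit to the Figure 2 schedule, or 36 to 40 over 18 to 20 participants.
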